6.6.2.3.3. Component Analysis

The components of the composite endpoint in patients not on tafamidis at baseline will be analyzed as follows. For all-cause mortality, Kaplan-Meier survival curves for each treatment group will be presented. The HR and corresponding 95% CI will be estimated from a Cox proportional hazards model including treatment as a covariate. Frequency of all-cause hospitalizations and urgent HF visits will be analyzed using Poisson regression with treatment, type of amyloidosis (hATTR vs. wtATTR), baseline NYHA class (I/II vs. III), and age at

randomization (<75 vs. ≥75 years) as covariates, adjusting for duration of follow-up (ie, include duration of follow-up as an offset).

6.6.2.4. Composite All-cause Mortality and Frequency of All-cause Hospitalizations and urgent HF visits over the 12-month Double-blind Period in the Overall Population

6.6.2.4.1. Definition of Estimand

The estimand is the same as that specified in Section 6.6.2.3.1, except the target patient population includes all patients with hATTR or wtATTR amyloidosis with cardiomyopathy (ie, patients may or may not be taking tafamidis at study entry).

6.6.2.4.2. Primary Analysis

The composite endpoint of all-cause mortality and frequency of all-cause hospitalizations and urgent HF visits will be analyzed using a modified Andersen-Gill model stratified by baseline tafamidis use (yes vs. no), including treatment, type of amyloidosis (hATTR vs. wtATTR), baseline NYHA class (I/II vs. III), and age at randomization (<75 vs. ≥75 years) as covariates.

6.6.2.4.3. Component Analysis

The all-cause mortality component of the composite endpoint will be evaluated using analyses similar to those described in Section 6.6.2.3.3. Frequency of all-cause hospitalizations and urgent HF visits will be analyzed using Poisson regression with treatment, baseline tafamidis use (yes vs. no), type of amyloidosis (hATTR vs. wtATTR), baseline NYHA class (I/II vs. III), age at randomization (<75 vs. ≥75 years), and the treatment-by-baseline tafamidis use interaction as covariates, adjusting for duration of follow-up (ie, include duration of follow-up as an offset).

6.6.3. Exploratory Endpoints

All analyses of exploratory endpoints will be conducted on the FAS. For continuous endpoints, descriptive statistics will be provided for actual value and change from baseline by treatment arm; descriptive statistics for percentage change from baseline by treatment arm may also be provided, as appropriate.

The composite endpoint of all-cause mortality and frequency of CV events (CV hospitalizations and urgent HF visits) over the 12m-DB period will be analyzed using a modified Andersen-Gill model similar to that for the composite endpoint of all-cause mortality and frequency of all-cause hospitalizations and urgent HF visits (see Section 6.6.2.4). The frequency of CV events component will also be analyzed using Poisson regression with treatment, baseline tafamidis (yes vs. no), type of amyloidosis (hATTR vs. wtATTR), baseline NYHA class (I/II vs. III), age at randomization (<75 vs. ≥75 years), and the treatment-by-baseline tafamidis use interaction as covariates, adjusting for duration of follow-up.

The change from baseline at Month 12 in select echocardiographic parameters (mean left ventricular [LV] wall thickness, LV relative wall thickness, LV mass, LV end-diastolic volume, global LV longitudinal strain, and cardiac output) and Norfolk QoL-DN Total Score (see Section 9.3.2) will be analyzed using an ANCOVA model since they are only measured in the 12m-DB period at Month 12. The ANCOVA model will include the baseline value for the

parameter as a continuous covariate and treatment arm, baseline tafamidis use (yes vs. no), type of amyloidosis (hATTR vs. wtATTR), age at randomization (<75 vs. ≥75), and the treatment-by-baseline tafamidis use interaction as covariates. The Norfolk QoL-DN questionnaire is a patient-reported outcomes measure that is sensitive to the different features of diabetic neuropathy; since patients enrolled in this study are not required to have a history of neuropathy, the ANCOVA model for Norfolk QoL-DN Total Score may be repeated on the subset of patients with a history of neuropathy.

In the 12m-DB period, NT-proBNP and troponin I are measured at baseline, Month 3, Month 6, Month 9, and Month 12, and mBMI is measured at baseline, Month 6, and Month 12. NT-proBNP, troponin I, and mBMI will be analyzed using MMRM models similar to the model described for the primary analysis of KCCQ-OS while adjusting for the baseline value of the endpoint being modeled (see Section 6.6.2.1). Assessments obtained on or after the onset of a serious COVID-19 AE will not be treated as missing.

NT-proBNP has been shown to be highly skewed in the literature; a Q-Q plot of the residuals of the NT-proBNP MMRM model specified above will be used to assess the normality assumption. If the normality assumption is violated, a natural log transformation (\log_e) will be applied to NT-proBNP to normalize the distribution. Following the transformation, an MMRM model similar to the model described for the primary analysis of KCCQ-OS will be used; the outcome variable will be $\log_e(\text{post-baseline}) - \log_e(\text{baseline})$, and the model will include $\log_e(\text{baseline})$ as a continuous covariate. Adjusted geometric mean fold-changes from baseline with 95% CIs will be constructed by exponentially back-transforming the LS means, differences in LS means, and the limits of the corresponding 95% CIs.

CMR and technetium scintigraphy will be performed in a subset of patients at select sites to assess cardiac amyloid involvement. The analyses for these imaging assessments are detailed in the separate APOLLO-B Imaging Statistical Analysis Plan.

Categorical exploratory parameters, including ATTR amyloidosis disease stage and NYHA class will be descriptively summarized by presenting the number and percentage of patients in each category for each visit. The number and percentage of patients with improving, no change, and worsening in these parameters at each visit will also be summarized.

Data collected during the OLE period will be summarized descriptively.

6.6.4. Subgroup Analysis

Subgroup analyses will be conducted to assess the consistency of treatment effect within various subgroups defined by the following baseline characteristics:

- Age [<75 ; ≥ 75 at randomization]
- Baseline tafamidis use [Yes; No]
- Type of amyloidosis [hATTR; wtATTR]
- NYHA class [I/II; III]

For subgroup analyses of 6-MWT, the effect size comparing treatment groups within each subgroup will be estimated using the HL estimate of the median difference between patisiran and placebo, together with its 95% CI. For each of the 100 complete datasets described in

Section 6.6.1.2, the HL estimate of the median difference between patisiran and placebo will be calculated within each subgroup, and the results will be combined by applying Rubin's rules, [Rubin 1996; Rubin 1987] using SAS PROC MIANALYZE to obtain the HL estimate and corresponding 95% CI for the subgroup. A forest plot will be generated to illustrate the estimated treatment effect along with 95% CI within each subgroup.

Subgroup analyses will be performed for KCCQ-OS using MMRM models. The baseline tafamidis use subgroup analysis will use the same MMRM model as specified in Section 6.6.2.1.2. For the other subgroup analyses, the outcome variable is the change from baseline in KCCQ-OS, and the model includes baseline KCCQ-OS as a continuous covariate and treatment arm, visit, baseline tafamidis use (yes vs. no), subgroup, the treatment-by-visit interaction, the treatment-by-subgroup interaction, the visit-by-subgroup interaction, and the treatment-by-visit-by-subgroup interaction as fixed factors. If the number of patients in either treatment arm of a subgroup category is less than 30, descriptive statistics may be presented. A forest plot will be generated to illustrate the estimated treatment effect along with 95% CI within each subgroup.

Other subgroups may be examined, if deemed appropriate. The subgroup analyses may also be performed for other efficacy endpoints.

6.7. Pharmacodynamic Analysis

The PD parameter for this study is serum TTR. For all analyses of post-baseline TTR data, only post-baseline TTR assessments collected within 24 days (inclusive) after receiving a full dose of study drug (ie, the amount infused was $\geq 80\%$ of the planned infusion volume) will be summarized.

Summary tables will be provided for observed values, changes and percentage changes from baseline for each scheduled time point by treatment arm.

The maximum percentage reduction and mean percentage reduction over 12 months will be summarized using descriptive statistics. Subgroup analysis will be provided for age (<65, 65 to <75, ≥ 75), sex (male vs. female), type of amyloidosis (hATTR vs. wtATTR), and baseline tafamidis use (yes vs. no). Other subgroups may be examined, if deemed appropriate.

All PD data will be displayed in data listings.

6.8. Pharmacokinetic Analysis

6.8.1. Study Variables

6.8.1.1. Concentration Data

Plasma concentrations of the 3 PK analytes (ALN-18328, DLin-MC3-DMA and PEG₂₀₀₀-C-DMG) will be obtained. Concentration values that are below the limit of quantification (LLOQ or BLQ) will be set to zero for analysis.

6.8.1.2. Pharmacokinetic Parameters

The following plasma concentrations of ALN-18328 and the two lipids will be summarized by study visit:

- Observed post-infusion peak concentration (C_{\max})
- Observed 30 min post-infusion concentration ($C_{p(30\text{min})}$)
- Observed pre-infusion trough concentration (C_{\min})

In addition, steady-state C_{\max} ($C_{\max_{ss}}$), steady-state C_{\min} ($C_{\min_{ss}}$) and steady-state $C_{p(30\text{min})}$ ($C_{p_{ss}(30\text{min})}$) will be calculated as the average of the C_{\max} , C_{\min} , and $C_{p(30\text{min})}$ values, respectively, at Week 24, Week 36, and Week 51.

6.8.2. Statistical Methods

Descriptive statistics for PK parameters will include the number of patients, mean, SD, SEM, coefficient of variation, median, minimum, maximum, geometric mean and geometric coefficient of variation.

The C_{\max} , $C_{p(30\text{min})}$ and C_{\min} of the 3 analytes will be summarized by nominal sampling day. Mean concentrations (+/- SD) will be plotted versus nominal sampling time.

Steady-state PK parameters for the 3 analytes will be summarized overall and by subgroup, including age (<65, 65 to <75, ≥ 75), sex (male vs. female), and anti-drug antibody status (positive vs. negative). Other subgroups may be examined, if deemed appropriate.

Plasma concentration data will be presented in by-patient listings.

The PK-PD relationship between the plasma concentration of ALN-18328 and the percent change from baseline in serum TTR may be explored.

Mean and maximum percent TTR reduction from baseline will be summarized by quartiles of the steady state PK parameters for the 3 analytes. Change from baseline at Month 12 in clinical efficacy parameters may also be summarized by quartiles of the steady-state PK parameters for the 3 analytes.

The incidence of AEs and serious AEs (SAEs) will be summarized by quartiles of the steady-state PK parameters for the 3 analytes.

Population PK, PK/PD, and disease progression modeling analyses may be performed, if appropriate. If performed, the analyses will be described in a separate analysis plan and reported separately.

6.9. Safety Analysis

An adverse event is any untoward medical event associated with the use of a study drug, whether or not it is considered related to the study drug. The primary safety parameter is the frequency of AEs. Safety parameters also include vital signs, ECGs, clinical laboratory assessments, and physical exams. Analyses for safety parameters will be conducted using the Safety Analysis Set.

Time windows for safety data to be analyzed for the 12m-DB period and the entire study including both 12m-DB and OLE periods as well as safety follow-up are described in Section 5.11. All safety data, regardless of time windows, will be listed and summarized for selected endpoints, ie, AEs by SOC and PT, SAEs by SOC and PT, and selected laboratory parameters.

Subgroup analysis for safety variables may be conducted if deemed appropriate and necessary.

No inferential safety analysis is planned.

6.9.1. Adverse Events

AEs will be classified by the MedDRA coding system (version 23.0 or later) and displayed in tables and data listings using SOC and PT.

Analyses of AEs will be performed for those events that are considered treatment-emergent, where treatment-emergent is defined as any AE with onset during or after the administration of study drug through 28 days following the last dose of study drug. In addition, any event that was present at baseline but worsened in intensity or was subsequently considered drug-related by the Investigator through the end of the study will be considered treatment-emergent. Events with a fully or partially missing onset date will be assumed to be treatment emergent unless it can be unequivocally determined (from the partial onset date and/or a partial or complete stop date) that the event occurred prior to the first administration of study drug.

Adverse events will be summarized by the numbers and percentages of patients reporting a given AE. A patient contributes only once to the count for a given AE (overall, by SOC, by PT). Overall event counts and frequencies may also be summarized.

An overall summary of AEs will include the number and percentage of patients with any AE, any AE assessed by the Investigator as related to treatment, any severe AE, any severe AE related to treatment, any SAE, any SAE related to treatment, any AE leading to treatment discontinuation, any study drug related AE leading to treatment discontinuation, and any deaths.

Tabulations by SOC and PT will be produced for the following. The SOC and PT within each SOC will be presented alphabetically.

- All AEs;
- Severe AEs;
- All SAEs;
- AEs related to treatment;
- SAEs related to treatment;
- AEs leading to infusion interruption;
- AEs leading to treatment discontinuation;
- SAEs leading to treatment discontinuation;
- AEs related to pre-medication;
- AEs over time.

Tabulations by PT in decreasing order in frequency in the patisiran arm will be produced for the following:

- All AEs;
- All SAEs;
- AEs related to treatment;

- SAEs related to treatment.

AEs will also be summarized by maximum severity and by maximum relationship; patients who report multiple occurrences of the same AE (preferred term) will be classified according to the most severe occurrence or the most related occurrence, respectively. Similarly, AEs related to treatment will be summarized by maximum severity.

Infusion-related reaction signs and symptoms will be summarized by SOC and PT. The incidence and frequency of IRR signs and symptoms over time will also be summarized by SOC and PT.

AEs mapping to the Drug Related Hepatic Disorder standardized MedDRA query (SMQ) will be summarized by SOC and PT. AEs mapping to the Anaphylactic Reaction SMQ will be summarized by PT. AEs mapping to the SMQ Malignant or Unspecified Tumors will be summarized by HLT and PT. Other SMQs or AE groupings may be evaluated.

All AEs will be presented in patient data listings. Separate listings will be provided for death, SAEs, AEs leading to treatment discontinuation, IRR signs and symptoms, AEs with missing severity, AEs with missing relationship to study drug, AEs related to pre-medications, and AEs mapping to the SMQs as described above.

Additional AE considerations regarding COVID-19 are detailed in Section 6.11.3.

Ophthalmological assessments may be performed if a patient develops ocular symptoms suggestive of vitamin A deficiency. The ophthalmological assessment results will be presented in a listing.

Patients who underwent heart transplant and/or ventricular assist device placement will be presented in a listing.

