2. STUDY OVERVIEW

2.1. Synopsis of Study Design

The APOLLO-B study is a multicenter, multinational Phase 3 study designed to evaluate the efficacy and safety of patisiran in approximately 300 patients with ATTR amyloidosis (hereditary or wt) with cardiomyopathy; the study is comprised of a 1:1 randomized, double-blind, placebo-controlled period of 12 months followed by an open-label extension (OLE) period of 36 months to evaluate the long-term safety and efficacy of patisiran.

The study design schema is presented in [Figure 1](#).

Figure 1: Study Design

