- Patisiran/Patisiran: all patients who received patisiran during the 12m-DB including patients who continued to receive patisiran during the OLE period and patients who discontinued treatment during the 12m-DB period;
- Placebo/Patisiran: all patients who received placebo during the 12m-DB period and switched to patisiran in the OLE period;
- All Patisiran: all patients who received at least one dose of patisiran during either the 12m-DB or OLE periods.

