5.6. Visit Windows

Scheduled visits are expected to follow the protocol schedule. All data will be tabulated and analyzed per the evaluation visit as recorded on the electronic case report form (eCRF) even if the assessment is outside of the visit window.

For 6-MWT and KCCQ, assessments will be conducted at baseline and at Months 6, 9, and 12 in the 12m-DB period and at Months 18, 21, 24, 30, 33, 36, 42 and 48 in the OLE period. For all longitudinal efficacy assessments, if a scheduled post-baseline assessment is not performed, assessments performed within ± 1.5 months of the scheduled assessment will be grouped with the scheduled assessments for that timepoint for analysis, with the following exception:

- For patients randomized to placebo who received patisiran in the OLE period, assessments performed after the first OLE dose will not be grouped with the scheduled Month 12 visits even if they are within ± 1.5 months.

The derived visits will be used for all analyses.

Unless otherwise specified above, data collected at unscheduled visits will be included in by-patient data listings and figures but no assignment to a study visit will be made for the purpose of by-visit summary tabulations. However, unscheduled visits may be used in the calculation of baseline values (as discussed in Section 5.4) and for inclusion in any categorical shift summaries (eg, shift from baseline to “worst” post-baseline value).

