5.11. Analyses for the Entire Study

The study design includes a 12m-DB period and an OLE period. The primary objective is to evaluate the efficacy and safety of patisiran compared with placebo during the 12m-DB period. In addition, the long-term efficacy and safety of patisiran during the entire patisiran treatment period (beyond 12m-DB) will be characterized for the All Patisiran Treated Set.

The detailed definitions for different treatment periods are as follows.

- **12m-DB Period**

The treatment comparison of patisiran versus placebo will focus on the 12m-DB period, defined as below:

1. For patients who received at least one dose of patisiran during the OLE period, all assessments collected prior to the first dose of patisiran in the OLE period will be included in the 12m-DB period. For patients randomized to patisiran, longitudinal efficacy assessments after the first OLE dose may be included in the 12m-DB period analyses as described in Section 5.6.
2. For patients who discontinued treatment and did not receive any patisiran doses in the OLE period, all assessments will be included in the 12m-DB period. Assessments collected within given time windows (details listed in below table) will be included in summary tables/figures and those outside the time windows will be listed only, unless otherwise specified (eg, AEs in Section 6.9).

Endpoint	Windowing rule for patients who did not enter OLE
Hospitalization/urgent HF visit/death	Events occurring on or before Day 417
Other efficacy endpoints	Assessments collected on or before Day 417
PK/PD endpoints	Assessments collected within 28 days of the last dose
Safety endpoints	Assessments with onset date within 28 days of the last dose ^a

^a In the rare situation where a patient did not discontinue treatment in the 12m-DB period and did not enter the OLE period, all data will be included in the summary tables/figures. For AE summaries, related AEs will be considered treatment-emergent and included in summary tables regardless of time window.

- **OLE Period**

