The start day of the OLE period is defined as the day when the first dose of the OLE period is administered. Unless otherwise specified, the assessments collected or AEs with onset date after the administration of the first dose in the OLE period will be included in the OLE period. When assessments or AE onset dates are exactly the date of first dose in the OLE period and the assessment or AE onset time is missing, the records will be included in the OLE period.

- **During Patisiran Treatment**

For all patients who received at least one dose of patisiran, data will be summarized for the “during patisiran treatment” period, defined as below.

1. For patients who received patisiran in the 12m-DB period, all assessments collected after the first dose of patisiran during the entire study, including both the 12m-DB and OLE periods (if available), will be included in the “during patisiran treatment” period.
2. For patients who received placebo in the 12m-DB period and switched to patisiran in the OLE period, all assessments collected after the first dose of patisiran in the OLE period will be included in the “during patisiran treatment” period.
3. For patients who discontinued patisiran treatment during the 12m-DB period, the data handling will follow the same rules as discussed above for “12m-DB period”. For patients who stopped participation in the study during the OLE period, assessments

collected within given time windows (details listed in below table) will be included in summary tables/figures and those outside the time windows will be listed only, unless otherwise specified (eg, AEs in Section 6.9). For ongoing patients, all data will be included.

Endpoint	Windowing rule for patients who discontinued patisiran in the OLE
Efficacy endpoints	Assessments collected within 90 days of the last dose
PD endpoint	Assessments collected within 24 days of the last dose
Safety endpoints	Assessments with onset date within 28 days of the last dose ^a

^a For AE summaries, related AEs will be considered treatment-emergent and included in summary tables regardless of time window.

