6.11.3. Impact on Adverse Events

An overall summary of AEs mapping to a COVID-19 custom query will include the number and percentage of patients, as well as events and event rates, with any AE, any AE assessed by the Investigator as related to treatment, any severe AE, any severe AE related to treatment, any SAE, any SAE related to treatment, any AE leading to treatment discontinuation, any study drug related AE leading to treatment discontinuation, and any deaths. AEs mapping to the COVID-19 custom query will be summarized by HLT and PT. Due to the evolving nature of COVID-19-related MedDRA terminology, the COVID-19 custom query will be based on the latest information available at the specified analysis timepoint.

AEs mapping to the COVID-19 custom query will also be presented in a data listing.

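### Long-term adverse event tables set crude percentages for up to 48 months on patisiran beside up to 36 months, with no exposure-adjusted rate and an undefined by-time table

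*SAP*

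**What the plan says.** All references are to the current plan, SAP Amendment 2.1.

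- **Design (2.1, 5.6).** The study has a "placebo-controlled period of 12 months followed by an open-label extension (OLE) period of 36 months". Walk-test and KCCQ visits in the extension run "at Months 18, 21, 24, 30, 33, 36, 42 and 48 in the OLE period".
- **Population (5.11).** Beyond the randomised comparison, "the long-term efficacy and safety of patisiran during the entire patisiran treatment period (beyond 12m-DB) will be characterized for the All Patisiran Treated Set".
- **Columns (5.2).** "Patisiran/Patisiran: all patients who received patisiran during the 12m-DB including patients who continued to receive patisiran during the OLE period", together with those who stopped during the double-blind period; "Placebo/Patisiran: all patients who received placebo during the 12m-DB period and switched to patisiran in the OLE period"; and All Patisiran, which pools the two.
- **Clock (5.11).** The on-patisiran period starts at the first double-blind dose for patients randomised to patisiran and at the first OLE dose for switchers. Patients who stop have a 28-day safety window after the last dose, except that related AEs count whenever they occur. "For ongoing patients, all data will be included".
- **Measure (6.9.1).** "Adverse events will be summarized by the numbers and percentages of patients reporting a given AE", with each patient counted once per AE. Event counts and frequencies are optional. A tabulation of AEs over time is required, but without time origin, intervals or denominator.
- **Elsewhere.** For the COVID-19 query, 6.11.3 requires patient percentages "as well as events and event rates". Section 6.4 summarises exposure separately from AEs. Section 6.9 plans no inferential safety analysis.

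**The concern.** A once-per-patient percentage grows with the time a patient is watched. It can be compared between two columns only if the columns cover similar observation time. Here they differ by a year by design, and months 36 to 48 on patisiran can be seen in one column only.

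Because no test is planned, readers will judge long-term safety by looking across these columns. A higher percentage under Patisiran/Patisiran could be read as a risk that builds up with exposure when it reflects only longer follow-up; a true late risk could equally be dismissed as follow-up. The table suited to telling these apart, AEs over time, is required but not defined.

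**Working it through.** **1. Follow-up, from the plan.** 12 + 36 = 48 months, which agrees with the last scheduled visit at Month 48 (5.6). Patients randomised to patisiran can have 48 months on drug. Switchers can have 48 − 12 = 36.

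**2. Crude percentage at equal risk.** The SAP gives no AE rates, so they are assumed: constant, equal in both columns, no dropout. The share with at least one event is 1 − exp(−r × T), with r per patient-year and T = 4 or 3 years. Gaps are from unrounded values.

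| Assumed rate r | 48 months | 36 months | Gap (points) |
|---|---|---|---|
| 0.01 | 3.9% | 3.0% | 1.0 |
| 0.05 | 18.1% | 13.9% | 4.2 |
| 0.10 | 33.0% | 25.9% | 7.0 |
| 0.30 | 69.9% | 59.3% | 10.5 |
| 0.50 | 86.5% | 77.7% | 8.8 |
| 1.0 | 98.2% | 95.0% | 3.1 |
| 2.0 | 100.0% | 99.8% | 0.2 |

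The gap exp(−3r) − exp(−4r) is largest at r = ln(4/3) = 0.288, where it is 68.4% − 57.8% = 10.5 points (unrounded values). For rare events the ratio of percentages tends to 48/36 = 1.33.

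**3. With dropout.** Assume an equal discontinuation hazard d = 0.10 per year. The share becomes r/(r + d) × (1 − exp(−(r + d)T)):

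- r = 0.05: 15.0% v 12.1%
- r = 0.10: 27.5% v 22.6%
- r = 0.30: 59.9% v 52.4%

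The gap shrinks but stays.

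**4. At an earlier cutoff.** The SAP gives no cutoff date. If ongoing patients had 18 v 6 months on patisiran (assumed), r = 0.30 gives 1 − exp(−0.45) = 36.2% v 1 − exp(−0.15) = 13.9%.

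**5. What a rate does under the same assumptions.** Expected first events divided by expected time at risk is (1 − exp(−rT)) ÷ [(1 − exp(−rT))/r] = r, whatever T is. Both columns give 10.0 per 100 patient-years at r = 0.10 and 30.0 at r = 0.30.

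**6. What a rate does when events cluster early.** Assume 20% of patients in each column have their event in month 1 (taken at mid-month, 0.04 years) and nobody later. Crude percentages agree, 20% v 20%. First events per 100 patient-years are:

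- 48 months: 0.2/(0.8 × 4 + 0.2 × 0.04) = 6.2
- 36 months: 0.2/(0.8 × 3 + 0.2 × 0.04) = 8.3
- 18 v 6 months: about 17 v 49

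Here the rate creates a false difference in the opposite direction. Neither measure is sufficient alone.

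**The case against.** **The tables are descriptive and the comparison is not an objective.** This stands. Section 5.11 centres the treatment comparison on the double-blind period, where planned follow-up is equal, and long-term safety is only characterised. Exposure in months is also reported, so a careful reader can see the difference. But the columns are still shown together, and the AE measure is not linked to that exposure.

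**A by-time tabulation is already required.** This stands too. A reader might infer that the plan has no means of separating a late-emerging risk from longer follow-up. The SAP does not support that: AEs over time must be produced. What is missing is its definition. Section 1 leaves table specifications to a separate document that is not at hand, and the definition may be there; the choice of denominator and time origin nevertheless belongs in the SAP.

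**The direction is not certain.** A reader might infer that Patisiran/Patisiran will show higher percentages. That needs equal, roughly constant hazards. The columns also differ by selection: Patisiran/Patisiran keeps patients who stopped during the double-blind period, while Placebo/Patisiran holds only those who reached the OLE. Very common AEs approach 100% in both.

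**No comparison of pooled patisiran with placebo is planned here.** A reader might fear that the All Patisiran column will be set against 12-month placebo. Section 5.2 lists three groups for this set, none of them placebo.

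**Rates are not a clean replacement.** Correct, as step 6 shows. They belong beside the percentages.

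**Conclusion.** The point holds as a low-cost improvement to the long-term safety tables. In the All Patisiran Treated Set, the committed crude percentages are not comparable between Patisiran/Patisiran and Placebo/Patisiran, and the by-time table that would help is undefined. Under assumed equal constant rates without dropout, follow-up alone produces gaps of up to about 10.5 points, and ratios up to about 1.33 for rare events. The figures illustrate the artefact; they do not forecast results, because 48 and 36 months are maxima and the rates are assumptions.

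The harm is to interpretation. No test, error rate or randomised comparison is affected. It would go too far to conclude that the long-term safety data are uninterpretable, or that rates should become the main measure.

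**What to change.** In 6.9.1, for the summaries during patisiran treatment in the All Patisiran Treated Set:

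1. Keep the crude percentages. Beside them, report patients with a first event per 100 patient-years at risk and total events per 100 patient-years, for AEs, SAEs and deaths. Derive time at risk from the 5.11 windows, not from the exposure end in 6.4 (last dose plus 20 days), which is shorter than the 28-day AE window. Leave related AEs outside the window out of the rate numerator, so that numerator and denominator cover the same time.
2. Define AEs over time by interval since first patisiran dose, with patients still under observation in each interval as the denominator. Early clusters then show as such, and months 36 to 48 are visibly from one group.

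The cost is SAP wording, a small extra time-at-risk derivation and wider tables. The rates assume a roughly constant hazard, which is why the interval table must accompany them. Neither change removes the selection of switchers who reached the OLE; a table footnote should say so.
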